#### 6.2.4 Previous and Concomitant Medications

Subjects taking the same medication multiple times will be counted once per medication and investigational period. A medication which can be classified into several chemical and/or therapeutic subgroups is presented in all chemical and therapeutic subgroups.

Previous medications are defined as medications that patients started and ended prior to first administration of study medication. Concomitant medications are defined as any medications that subjects took after the first dose of study medication and through Follow-up period (EoS). Medications that started prior to first administration of study drug and continued while study drug was given will be counted in both previous and concomitant medications.

Previous and concomitant medications are coded with WHO-Drug Global data and will be provided in listing format by site and subject for the All Randomized Set.

### 6.3 Study Drug Exposure and Compliance

As per study schedule, all subjects will be assigned to either 'Mirabegron 25 mg' or 'Mirabegron 50 mg' at visit 2/week 0.

At visit 3/week 4 or visit 4/week 8 subjects can be up-titrated from 'Mirabegron 25 mg' to 'Mirabegron 50 mg' until the end of the study. Once up-titrated the dose cannot be adjusted back down. Study drug exposure will be summarized for the following groups:

- Mirabegron 25 mg
  - Never Up-Titrated
  - Later Up-Titrated to 50 mg
  - Total
- Mirabegron 50 mg
  - as Randomized

- Up-Titrated from 25 mg
- Total

#### 6.3.1 Exposure

The following information on drug exposure will be presented by treatment groups described in Section 6.3 for the SAF:

- Descriptive statistics for cumulative amount of the drug to which the subject was exposed; and
- Number and percent of subject with dose increases or interruptions.

Duration of exposure will be summarized in two ways.

- Descriptive statistics will be presented by treatment group.
- Exposure time will be categorized according to the following categories by treatment group:
  - at least 1 day, less than 7 days
  - at least 7 days, less than 14 days
  - at least 14 days, less than 28 days
  - at least 28 days, less than 56 days
  - at least 56 days, less than 83 days
  - 84 days or more
  - Unknown.
- Counts and percentages of cumulative exposure will be categorized according to the following categories by treatment group for the SAF:
  - $\circ \geq 7 \text{ days}$
  - $\circ \geq 14 \text{ days}$
  - $\circ \geq 28 \text{ days}$
  - $\circ \geq 56 \text{ days}$
  - $\circ \geq 84 \text{ days}$

Exposure details will be listed for each subject by study visit and total for all randomized subjects.

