## 5.5 Other Endpoints

### 5.5.1 Exposure to Study Drug

The duration of exposure to each dose of study drug (Mirabegron 25 mg and Mirabegron 50 mg) by visit and for the whole period will be calculated using the following information :

- Overall start date and stop date of the study medication. The first dose of study drug is to be administered on Day 1, the day on visit 2/week 0 [baseline]. Treatment will be administered once daily orally after meal during a 12-week, open-label treatment period.
- Start date and new dose of study drug at each titration step. At visit 3/week 4 or visit 4/week 8 the dose may be up-titrated (from 25 to 50 mg according to investigators' discretion), or may remain the same. The study does not allow dose reduction from 50 mg to 25 mg as the former is considered a safe and effective recommended dose.

- Start date and new dose of study drug after each unscheduled dose change.
- At any time during the treatment period, the subject may have an unscheduled dose interruption. At each unscheduled change in dose, the (new) dose, start date and reason are recorded.

In all cases where there is a dose change, either because of dose titration or an unscheduled dose interruption, the first and the last dose of the medication at the old level will be collected at the CRF. In this way, the subject's dosing history can be reduced to a series of unbroken intervals within each of which, the dose level is constant. From these, the subject's exposure at each dose can be calculated.

To illustrate, consider a subject with the following dose information on the eCRF:

- The dates of the very first and very last dose of the study medication given at  $D_1=1^{st}$  July 2020,  $D_{last}=23^{rd}$  September 2020.
- Up-titration to 50 mg at Visit 3. The first dose at the new level is given at  $D_2=29^{th}$  July 2020.
- Study drug interrupted at an unscheduled visit. The date of last dose is given at D3=1st August 2020.
- Study drug re-started at an unscheduled visit at  $D_4=5^{th}$  August 2020.
- Remains at 50 mg till Visit 5 (Dlast=23rd September 2020).

From these dates we calculate the following:

- The duration of exposure to the treatment can be calculated as  $E_{TOT}=D_{last}-D_1+1-(D_4-D_3-1)$ =82 days.

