# **6 STATISTICAL METHODOLOGY**

## 6.1 General Considerations

Continuous data will be summarized descriptively including the number of subjects (n), mean, standard error of the mean (SEM) (efficacy data), standard deviation (SD), median, minimum and maximum. Categorical data will be summarized by frequencies and percentages. Percentages by categories will be based on the number of subjects with no missing data, i.e., the percentages for the non-missing categories will add up to 100%.

All statistical comparisons will be conducted using 2-sided tests at the 5% significance level unless stated otherwise. All null hypotheses will be of no treatment difference, all alternative hypotheses will be two-sided, unless specifically stated otherwise.

All data summarization and analyses will be performed using SAS® Version 9.4 or higher on Linux. Specifications for table, figures, and data listing formats can be found in the TLF specifications.

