Additionally, for groups with both a baseline and week 12 measurement (i.e., Mirabegron 25 mg [Never Up-Titrated], Mirabegron 50 mg [As-Randomized] and Total Mirabegron) a within-subject change will be calculated as the post-baseline measurement minus the baseline measurement and summarized in the same way. Each laboratory result will be classified as low (L), normal (N), or high (H) at each visit according to the laboratory supplied reference ranges.

The number and percentage of subjects below and above reference range will be summarized by treatment group and visit.

Frequency tabulations of qualitative clinical laboratory variables (urinalysis) will be presented by treatment group and visit.

Summary shifts of reference range (low, normal, high) changes from baseline to week 12 will be presented by the following treatment groups:

- Mirabegron 25 mg (Total)
- Mirabegron 50 mg (As-Randomized)
- Total Mirabegron, i.e., the sum of the Mirabegron 25 mg (Total) and of Mirabegron 50 mg (As-Randomized).

These shifts are categorized as:

- "Shift to Low": shift from normal or high to low
- "Shift to High": shift from normal or low to high
- "Categorized Increase": shift from low to normal or from normal to high
- "Categorized No Change": value stays in the same reference range
- "Categorized Decrease": shift from high to normal or from normal to low.

All clinical laboratory data collected during the study and variables derived from it will be listed using SAF.

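### SAP 6.3.1's exposure categories skip exactly 83 days; as a lesser point, SAP 6.5.2 leaves two-step laboratory shifts out of its Increase / No Change / Decrease split

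*SAP*

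**What the plan says.** **Exposure.** SAP 6.3.1 tabulates duration of exposure in six numeric bands plus Unknown. Up to the fourth band, each upper bound is the next lower bound; for example, "at least 28 days, less than 56 days" is followed by a band that starts at 56. The last two are "at least 56 days, less than 83 days" and "84 days or more". A separate cumulative list in the same section uses cut-points of 7, 14, 28, 56 and 84 days. SAP 6.1 bases percentages on subjects without missing data, so that "the percentages for the non-missing categories will add up to 100" percent.

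**Laboratory shifts.** SAP 6.5.2 defines five labels for the change in reference-range class from baseline to week 12. Shift to Low covers normal or high to low, and Shift to High covers normal or low to high. Categorized Increase is "shift from low to normal or from normal to high", Categorized Decrease is "shift from high to normal or from normal to low", and Categorized No Change means staying in the same range.

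**The concern.** A set of exclusive bands should give every known duration one place. Here a subject treated for 83 days, one day short of the planned 12 weeks, has none. Unknown does not fit, because the duration is known. The programmer must leave the subject out of every row, use Unknown wrongly, or choose a neighbouring band without authority from the SAP. The first choice breaks the rule in SAP 6.1; the other two are undocumented decisions. The subjects concerned are mostly people who completed treatment within the visit window, in a study whose stated purpose includes safety surveillance.

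The laboratory labels have a similar but milder gap. The two largest changes of class, low to high and high to low, carry no direction-of-change label, although they are plainly an increase and a decrease.

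**Working it through.** **1. Unit of exposure.** SAP 5.5.1 gives a formula ("The duration of exposure to the treatment can be calculated as" last date − first date + 1, less interrupted days) and a worked example:

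- 1 July to 23 September 2020 inclusive: 85 calendar days.
- Last dose before the interruption 1 August, restart 5 August: 3 days interrupted.
- Total: 85 − 3 = 82 days, as the SAP states.
- By dose: 28 days at 25 mg; 4 + 50 = 54 days at 50 mg. These also match.

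Exposure is therefore a whole number of days, and it is split by dose.

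**2. Coverage of the bands.** Every whole day from 1 to 119 was tested against the six numeric bands. Only 83 falls in none, and no day falls in two.

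**3. Is 83 reachable?** SAP 5.5.1 states: "Treatment will be administered once daily orally after meal during a 12-week, open-label treatment period". Twelve weeks is 12 × 7 = 84 days. Protocol Table 1 allows ±3 days at Visit 5. Around the Day 84 target in SAP Table 5 this spans Days 81–87; counted as 12 full weeks after Day 1 it spans Days 82–88. Both include 83. SAP 5.5.2 assumes a tablet on the Visit 5 day, so a Visit 5 on Day 83 with no interruption gives 83 days. A short interruption can do the same, for instance 85 − 2.

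**4. Who can be affected?** SAP 6.3 presents exposure by dose group. A 25 mg subject escalated on schedule at week 4 or week 8 has roughly 28 and 56 days on the two doses, in one order or the other, and so does not reach 83 on either. That leaves the 50 mg as-randomized group and the never-up-titrated 25 mg subjects.

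**5. Scale.** Assume that completers' last doses are spread evenly over the 7-day window, and that the 25% dropout used to size the 50 mg group applies to both arms.

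- 50 mg: 166 × 0.75 = 124.5, the plan's 125; 125 / 7 = 17.9, about 18.
- 25 mg: 249 − 166 = 83 randomized; 83 × 0.75 = 62; 62 / 7 = 8.9, about 9 if nobody escalates.

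**6. Laboratory labels, all nine cells.**

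| Baseline → week 12 | Shift label | Direction label |
|---|---|---|
| low → low | none | No Change |
| low → normal | none | Increase |
| low → high | Shift to High | **none** |
| normal → low | Shift to Low | Decrease |
| normal → normal | none | No Change |
| normal → high | Shift to High | Increase |
| high → low | Shift to Low | **none** |
| high → normal | none | Decrease |
| high → high | none | No Change |

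Seven of the nine cells have exactly one direction label; the two two-step cells have none.

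**7. After correction.** With the fifth band ending below 84, no day from 1 to 119 is uncovered or double-counted. With low to high added to Increase and high to low added to Decrease, all nine cells have exactly one direction label.

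**The case against.** The strongest reply is that the exposure gap is an obvious one-digit slip with little consequence. The 12-week period and the cumulative cut-point both point to 84. An 83-day subject is still in the descriptive statistics, in the by-subject listing and in the cumulative row for 56 days or more. Table formats are set in separate specifications that are not among these documents and may already have it right. All of that stands, and it limits the importance. It does not remove the defect: the SAP is the governing text, and its literal rule yields a table that contradicts SAP 6.1.

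On the laboratory side, the reply is that the five labels were never a partition. Normal to high, for example, carries both a Shift label and a direction label, and the SAP does not say that Increase, No Change and Decrease must be exhaustive. This also stands. A reader might infer from the definitions that two-step shifts vanish from the shift summary. The documents do not support that: they are counted under Shift to High and Shift to Low, they enter the counts below and above range by visit, and all laboratory data are listed. What remains is an incomplete direction split.

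A reader might also apply the one-in-seven share to all completers: 249 × 0.75 = 187, and 187 / 7 = 27. That base is wrong for a table laid out by dose. The figure of 27 would need every 25 mg subject to stay on 25 mg, and the documents give no escalation rate.

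**Conclusion.** The exposure gap is real: exactly 83 days fits no category in SAP 6.3.1, and the value lies inside the Visit 5 window. Under an even spread over seven days and 25% dropout in both arms, about 18 of 125 completers in the 50 mg as-randomized group would be unplaced, plus at most about 9 never-up-titrated 25 mg subjects. The even spread is an assumption that gives a sense of scale and is not taken from the documents; the numbers are smaller if visits cluster on the target day itself. The conclusion does not depend on them, since one such subject is enough to break the total.

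The laboratory point is secondary. The direction split omits low to high and high to low, while the same list counts both elsewhere. No count is estimated, because the documents give no basis for one.

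Both points are minor. They concern descriptive safety tables only; the primary efficacy analysis, the other efficacy results and the adverse event counts are unaffected.

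**What to change.** - **SAP 6.3.1:** change the upper bound of the fifth exposure category from below 83 to below 84 days, in line with the cumulative 84-day cut-point.
- **SAP 6.5.2:** add low to high to Categorized Increase and high to low to Categorized Decrease. Shift to High and Shift to Low need no change.
- Check that the table specifications and programs use the same bounds and labels.

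The cost is two wording corrections and a check of the programs. No data, sample size or design feature changes. SAP section 1 allows revisions up to database hard lock; after that, the correction can be recorded in the clinical study report.

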#### 6.3.2 Treatment Compliance

Total compliance with the dosing schedule will be examined for subjects in the SAF whose total study drug count and first and last days of treatment are known.

Percent total compliance will be summarized in two ways for the SAF:

- Descriptive statistics will be presented by treatment group.
- Percent compliance will be categorized according to the following categories by treatment group:
  - less than 70%
  - $\circ~$  at least 70%, less than 80%
  - at least 80%, less than 120%
  - at least 120%

• Unknown.

Treatment compliance details, including all data relevant to the calculation, will be listed for each subject by study visit and total for all randomized subjects.

# 6.4 Analysis of Efficacy

Efficacy analysis of the data from Mirabegron 50 mg group will be conducted on the FAS, and interpretation of results from statistical tests will be based on the FAS as well.

No multiplicity adjustment will be necessary in this study.

Efficacy data will be summarized by visit (week 0, 4, 8 and 12) and by EoT values unless otherwise specified.

All inferential statistics will be presented by the following treatment groups:

- Mirabegron 25 mg (Total)
- Mirabegron 50 mg (As-Randomized)

All summary descriptive statistics will be presented by the following treatment groups:

- Mirabegron 25 mg
  - Never Up-Titrated
  - Later Up-Titrated to 50 mg
  - Total
- Mirabegron 50 mg
  - $\circ$  as Randomized
  - Up-Titrated from 25 mg
  - Total

### 6.4.1 Analysis of Primary Efficacy Endpoint

The primary efficacy endpoint is change from baseline to week 12 in mean number of micturitions per 24 hours in Mirabegron 50 mg group.

### 6.4.1.1 Primary Analysis for Primary Efficacy Endpoint

The primary estimator for the primary estimand as defined in [Section 2.1.1 Estimand] will be calculated according to the evaluation of the primary efficacy endpoint. The primary efficacy endpoint will be analyzed using a Mixed Models Repeated Measures (MMRM). The MMRM model will include visit (the repeated term), treatment group (25 mg [total] or 50 mg [as-randomized]), pooled site, sex and the interaction between treatment group and visit as fixed effects and baseline measurement (the mean number of micturitions per 24 hours) as covariate. The algorithm to pool sites will be generated and documented prior to data base lock (Appendix 9.1). If the inclusion of pooled sites creates modeling problems, then dropping that factor will be considered. Subject will be identified as subject in the repeated statement.

The hypothesis for comparisons is given as follows:

- H0: The adjusted mean change from baseline at week 12 in mean number of micturitions per 24 hours in the 50 mg group is not different from zero.
- H1: The adjusted mean change from baseline at week 12 in mean number of micturitions per 24 hours in the 50 mg group is not equal zero.

Statistical testing will be done 2-sided at a 5% significance level.

The MMRM model results will be presented by treatment least squares (LS) means ( $\pm$  standard error [SE]) along with 2-sided 95% confidence intervals (CIs) and associated p-value for mean changes from baseline at weeks 4, 8 and 12 (the primary endpoint). Data from subjects who switch from 25 to 50 mg mirabegron will not be included in MMRM model. Data from those subjects prior to switching will still be included in the MMRM model with treatment equal to 25 mg.

Model fitting will be visually assessed. A scatter plot of residuals versus predicted values, along with histogram and normal probability plots will be produced.

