9.4.2.1 Analysis of Primary Endpoint

9.4.2.1.1 **Primary Analysis**

The primary efficacy endpoint change from baseline in mean micturitions per 24 hours will be analyzed using a Mixed Models Repeated Measures (MMRM). The MMRM model will include visit (the repeated term), treatment group (25 mg or 50 mg), pooled site, sex, and the interaction term between treatment and visit as fixed effects and baseline measurement (mean number of micturitions per 24 hours) as covariate. If necessary, pooled centers will be generated and documented prior to database lock. If the inclusion of pooled centers creates modeling problems, then dropping that factor will be considered. Subject will be identified as subject in the repeated statement. By treatment least squares (LS) means (\pm standard error [SE]) along with 2-sided 95% CIs will be presented for changes at weeks 4, 8 and 12 (the primary endpoint). Consistent with the estimand described in section 3, data from subjects who switch from 25 to 50 mg mirabegron will be summarized only after switching, not included in MMRM model. Data from those subjects prior to switching would still be included in the MMRM model.

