# **3** SAMPLE SIZE

The sample size for this study is based upon change from baseline for mean number of micturitions/24 hours within a single treatment arm. Change from baseline will be tested to determine if the change is different from zero i.e., a change in mean number of micturitions/24 hours. When the sample size is 125, a single group t-test with a 5% two-sided significance level will have 80% power to detect a change of 0.9 micturitions with a SD of 3.562 [Neurourology and Urodynamics, 2015]. Assuming 25% of the subjects will drop out, about 166 subjects will be enrolled to yield 125 evaluable subjects in 50 mg group.

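### The primary MMRM imposes one baseline slope on all visits; the one-arm 50 mg Week 12 mean may be biased if dropout depends on baseline and that slope changes over visits

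*SAP*

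**What the plan says.** SAP 6.4.1.1 names visit, treatment group, pooled site and sex, followed by "the interaction between treatment group and visit as fixed effects and baseline measurement", the last of these being the covariate. Protocol 9.4.2.1.1 has the same structure: "the interaction term between treatment and visit as fixed effects and baseline measurement (mean number of micturitions per 24 hours) as covariate". In both documents treatment-by-visit is the only interaction, and baseline is a main effect.

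The null hypothesis concerns one arm, with zero as the reference value: "The adjusted mean change from baseline at week 12 in mean number of micturitions per 24 hours in the 50 mg group is not different". On the level, the SAP says "Statistical testing will be done 2-sided at a 5% significance level".

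The sample size section (SAP 3) plans for loss: "Assuming 25% of the subjects will drop out, about 166 subjects will be enrolled to yield 125 evaluable subjects in 50 mg group". SAP 6.10.2 rules out imputing missing outcome values as a general principle, so the MMRM carries the missing-data assumption alone. Model fit is judged from residual plots (SAP 6.4.1.1). The only sensitivity analysis mentioned is an optional one without outliers (SAP 6.10.3). SAP 6.4.2.1 reuses the model for the secondary endpoints, each with its own baseline, and SAP 6.4.1.3 reuses it for the prior-treatment subgroups.

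**The concern.** With baseline as a main effect only, the fitted slope is a compromise across the three visits, weighted toward the visits with more data and less variance. If the true slope at Week 12 is steeper than at Week 4, the compromise is too shallow for Week 12. If the subjects still present at Week 12 also differ in baseline from the full analysis set (FAS), the Week 12 LS mean is carried from their mean baseline to the overall mean baseline along the wrong slope.

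In a contrast between arms most of that error would cancel. Here the primary quantity is one arm against zero, so the error passes into the estimate, the CI and the p-value. It can arise even when missingness depends only on baseline, which is in the model. If high-baseline subjects leave more often and the slope steepens, the fall in micturitions is understated. If low-baseline subjects leave more often, it is overstated. None of the planned checks is aimed at this.

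**Working it through.** **1. The plan's own figure.** SAP 3 starts from this design: "When the sample size is 125, a single group t-test with a 5% two-sided significance level". The claim made for it is that it "will have 80% power to detect a change of 0.9 micturitions with a SD of 3.562". With the noncentral t distribution, the smallest n reaching 80% is 125 (power 0.8004), so the figure reproduces. For dropout, 125/0.75 = 166.7, against about 166 planned (166 × 0.75 = 124.5). No stated number is wrong. The planning SE is 3.562/√125 = 0.319.

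**2. Form of the bias.** Approximately:

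bias ≈ (Week 12 slope − fitted common slope) × (completers' mean baseline − overall mean baseline)

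It vanishes if either factor is zero. Within-subject correlation modifies it somewhat.

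**3. Both factors are needed.** Large-sample runs used 150,000 subjects, 2:1 arms, baseline SD 3.5, correlation 0.6, unstructured covariance and 25% dropout depending on baseline only. Overall mean baseline is set to 0.

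| True slopes, Weeks 4/8/12 | Dropout OR per SD | Fitted slope | Completers' baseline | Formula | Bias, common slope | Bias, baseline-by-visit |
|---|---|---|---|---|---|---|
| -0.5/-0.5/-0.5 | 2 | -0.503 | -0.549 | 0.003 × -0.549 = -0.002 | -0.006 | -0.005 |
| -0.3/-0.4/-0.5 | 1 | -0.399 | 0.007 | -0.101 × 0.007 = -0.001 | -0.000 | -0.001 |
| -0.3/-0.4/-0.5 | 2 | -0.397 | -0.566 | -0.103 × -0.566 = +0.058 | +0.078 | -0.002 |

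With equal slopes, or with dropout unrelated to baseline, the two models agree within simulation noise. They separate only in the third row.

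**4. Behaviour at trial size.** 166 + 83 subjects, baseline SD 3.0, 1,000 repetitions per setting; each cell is common slope versus baseline-by-visit.

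| Slopes; dropout OR | Week 12 bias (true change 0) | Type I error | Power at -0.9 |
|---|---|---|---|
| -0.5 throughout; 2 | 0.01 vs 0.01 | 5.1% vs 5.0% | 89.7% vs 88.9% |
| -0.3/-0.4/-0.5; 2 | 0.06 vs -0.01 | 6.8% vs 6.1% | 84.1% vs 87.8% |
| -0.2/-0.35/-0.5; 3 | 0.15 vs 0.00 | 9.3% vs 6.3% | 75.8% vs 87.5% |

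Simulation error is about 0.7 points on type I error and 1.0 to 1.4 on power.

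**5. Allowing for the FAS.** SAP 4.3 requires at least one post-baseline micturition measurement, so subjects lost before Week 4 leave both the analysis and the mean baseline. Assumed inputs: baseline SD 3, residual correlation 0.65, Week 12 slope 0.2 to 0.4 steeper than Week 4, OR 1.5 to 3, 25% total loss.

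- A third of the loss before Week 4: bias about 0.04 to 0.13.
- All loss after Week 4: about 0.06 to 0.23.
- With baseline-by-visit: about 0.01 or less.

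Against the design effect: 0.04/0.9 = 4%, 0.13/0.9 = 14%, 0.23/0.9 = 26%. Against the planning SE: 0.04/0.319 = 0.13, 0.13/0.319 = 0.41, 0.23/0.319 = 0.72.

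**6. Effect on the test.** If the true change is -2.0, the largest bias gives (-2.0 + 0.23)/0.319 = -5.5, still far from zero. At -0.9, a bias of 0.13 moves the expected ratio from -0.9/0.319 = -2.82 to -0.77/0.319 = -2.41.

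**Not in the documents, hence assumed:** baseline SD, slopes, dropout odds ratio, correlation, timing of loss and an unstructured covariance. Site and sex were left out of the simulations. The LS mean was taken at the subject-level mean baseline, which the SAP does not specify.

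**The case against.** A reader might infer that baseline-dependent dropout alone biases the primary estimate, or that the estimate is biased as planned. The documents support neither reading. With equal slopes the planned model is unbiased under baseline-dependent dropout, and the documents give no slope by visit, no baseline SD and no link between dropout and baseline.

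The slope premise is also demanding. With baseline SD 3 and residual SDs of 2.4 at Week 4 and 3.0 at Week 12, slopes of -0.3 and -0.5 imply that the correlation with baseline falls from 2.1/√(2.1² + 2.4²) = 0.66 to 1.5/√(1.5² + 3.0²) = 0.45 in eight weeks. Slopes of -0.2 and -0.6 imply a fall from 0.71 to 0.37. Entry requires at least 8 micturitions/24 h (Protocol 5.1), and regression to the mean from that selection can already show at Week 4. Steepening after Week 4 is therefore plausible but not given.

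The 25% is a planning allowance. Subjects who stop treatment stay in follow-up (Protocol 8.1, 8.2), and the Week 12 diary window runs from Day 71 to Day 97 (SAP 6.10.1), so actual loss may be smaller. With 15% total loss spread evenly over the three intervals and an odds ratio of 1.5, the two models differ by only 0.02 to 0.04.

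Finally, the change would come late. The study is open-label, SAP 9.1 records 249 subjects as already randomized, and the primary analysis may be run at a data cut (SAP 6.9). This argues for a documented, pre-specified change and against an informal one. It does not remove the gap in the model. The points on size and on the two conditions stand and are reflected in the verdict.

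**Conclusion.** The concern holds in conditional form. The model forces a common baseline slope, and the one-arm test gives the resulting error nothing to cancel against. Bias in the 50 mg Week 12 LS mean needs both baseline-dependent dropout and a slope that changes across visits, and neither is established. Under the assumptions listed, the more realistic range is about 0.04 to 0.13 micturitions/24 h, rising to about 0.23 if no subject is lost before Week 4. The upper ends depend on how loss is spread over the intervals and are approximate.

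A reader might also infer that the primary conclusion is in doubt. That does not follow: a change near -2 stays significant, and the accuracy of the estimate and CI is what is mainly at stake. Type I error is clearly inflated only in the harsher simulated case (odds ratio 3); in the moderate case the difference is within simulation error. This is a worthwhile, cheap improvement to the model and leaves the stated sample size untouched.

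**What to change.** Add baseline-by-visit to the MMRM in SAP 6.4.1.1, and so in 6.4.2.1, giving: visit, treatment, treatment-by-visit, pooled site, sex, baseline, baseline-by-visit. Hypothesis, estimand and LS-mean reporting stay the same. In the same edit, state the baseline value at which LS means are evaluated, because the interaction does not settle that.

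SAP 1 allows version-controlled revision before hard lock. Because Protocol 9.4.2.1.1 names the model without this term, record the departure and justify it in the CSR (Protocol 9.4). If the primary model is regarded as fixed, for example because a data cut has been analysed, pre-specify the interaction model as a sensitivity analysis instead.

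The cost is two extra parameters, a Week 12 SE about 1% larger if slopes are in fact equal (0.250 to 0.252; 0.252/0.250 = 1.008), and a documented difference from the protocol model.
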